1.3.2 Visit 10 through Visit 19 **CCI**

Table AMAX.1 2. Schedule of Activities - Visit 10 through Visit 19 **CCI**

Procedures	Schedule of Activities ^a													
	V10	V11	V12		V13	V14		V15	V16		V17	V18	V19	
Visit Number	Office	Office	Phone	Office	Office	Phone	Office	Office	Phone	Office	Office	Office	Phone	Office
Visit Type	Office	Office	Phone	Office	Office	Phone	Office	Office	Phone	Office	Office	Office	Phone	Office
Week Relative to Study Drug Start ^b	CCI													
Day with Visit Tolerance Interval (VTI)	CCI													
All Participants (X); AMAM Rollover Participants Only (M); AMAG Rollover Participants Only (G); Optional (Opt) (See footnotes for additional key details)														
TB Risk Assessment Monitoring ^f	X	X		X	X		X	X		X	X	X		X
Yearly screening for active and latent TB in participants in the Czech Republic*							X							X

Abbreviations: AEs = adverse events; CT = computed tomography; CXR = chest x-ray; IGRA = interferon gamma release assay; TB = tuberculosis; TST = tuberculin skin test; V = visit.

* Participants from the Czech Republic will be screened for active and latent TB infection annually, including at Visits 14 and 19. This will include assessment of medical history, AEs and clinical risk, physical examination, and a TB test as described in Tuberculosis Testing section (Section 8.2.6 of main protocol and Section 8.2.6 of this appendix). Participants who had a TST must return 48 to 72 hours after placement to have their test results read by a pulmonologist. A chest X-ray may be performed if clinically indicated. A CT scan may be performed as an alternative based on regional standard of practice.

a Please see detailed instructions provided by the sponsor for calculation of visit dates. Also, note that unscheduled assessments can be performed during scheduled visits, see Table AMAX.1-3 for details. Please refer to Section 10.13.3 for the optional continued access period details. Participants from the Czech Republic will continue to be screened for active and latent TB infection annually during continued access if they participate.

- b All activities should be completed prior to any study drug administration unless otherwise stated.
- c Site to remind participant to complete 14-Day diary and/or bowel prep, as appropriate. Phone reminder must occur at least 15 days prior to actual next visit date to ensure the participant begins the collection of diary data in time.
- f Throughout the study, participants will be assessed for risk factors for TB (Section 10.5, Appendix 5). If the participant has a risk factor(s) or any TB-related signs or symptoms identified as part of the discussions of AEs or as part of the standard physical exam, the investigator should conduct a thorough exam to evaluate for TB, including examination of peripheral lymph nodes and documentation of body temperature. If there are relevant physical findings or other factors that the investigator feels warrant testing and imaging, an IGRA or TST and CXR should be performed ([Table AMAX.1-3 Unscheduled assessments](#)). A CT scan can be performed as an alternative to the CXR based on regional standard of practice (Section 8.2.6).

5.1 Inclusion Criteria

[6] b. Female Participants:

Women of **childbearing potential** (WOCBP, defined as all adult females unless they are WNOCBP as defined below) may participate if they meet the following criteria:

A. must test negative for pregnancy prior to initiation of treatment as indicated by a negative urine pregnancy test at Visit 1/Week 0 of this study within 24 hours prior to exposure

AND

B. must agree to either remain abstinent, if complete abstinence is their preferred and usual lifestyle, or remain in same-sex relationships, if part of their preferred and usual lifestyle, without sexual relationships with males. Periodic abstinence (for example, calendar, ovulation, symptothermal, or postovulation methods), declaration of abstinence just for the duration of a trial, and withdrawal are not acceptable methods of contraception,

OR

must use a combination of 2 effective methods of contraception or 1 highly effective method of contraception for the entirety of the study, where at least 1 method must be highly effective and the other method is effective or highly effective. Abstinence or contraception must continue following completion of study drug administration for **16 weeks**.

- i. Effective methods of contraception may include barrier methods such as male or female condoms with spermicide, diaphragms with spermicide, or cervical sponges (which usually are made with spermicide). The barrier method must include use of a spermicide to be counted as one effective method.
- ii. At least one highly effective method of contraception must be used. A highly effective method of contraception is defined as one with a Pearl index <1 (which is used to measure the reliability of birth control methods), such as male or female sterilization, hormonal birth control like the Pill (with the exception of Mini Pill), 3-month injection, hormone implantation, hormone loop, vaginal ring, or transdermal patch. Highly effective (<1% failure rate) methods of contraception include
 - ~~female sterilization~~
 - ~~combination oral contraceptive pill~~
 - ~~progestin only contraceptive pill (mini pill)~~
 - ~~implanted contraceptives~~
 - ~~injectable contraceptives~~
 - ~~contraceptive patch (only women <198 pounds or 90 kg)~~
 - ~~vasectomy (if only sexual partner)~~
 - ~~fallopian tube implants (if confirmed by hysterosalpingogram)~~
 - ~~combined contraceptive vaginal ring, or~~
 - ~~intrauterine devices.~~

iii. Ineffective forms of contraception, whether used alone or in any combination, include

- spermicide alone
- periodic abstinence
- fertility awareness (calendar method, temperature method, cervical mucus, or symptothermal)
- withdrawal
- postcoital douche, or
- lactational amenorrhea.

Women **not of childbearing potential** (WNOCBP) may participate and include those who are:

A. infertile due to surgical sterilization (total hysterectomy, bilateral salpingo-oophorectomy, bilateral salpingectomy, bilateral oophorectomy, or tubal ligation)^a, have a congenital anomaly such as Müllerian agenesis,

OR

B. postmenopausal^b – defined as either:

- i. a woman at least 40 years of age with an intact uterus, not on hormone therapy, who has had either
 - cessation of menses for at least 1 year, without an alternative medical cause
 - at least 612 months of spontaneous amenorrhea with a follicle-stimulating hormone (FSH) level >40 mIU/mL
- ii. a woman 55 years or older not on hormone therapy, who has had at least 612 months of spontaneous amenorrhea, or
- iii. a woman at least 55 years of age with a diagnosis of menopause prior to starting hormone replacement therapy.

^a Note that if it has been less than 6 weeks post-surgical bilateral oophorectomy with or without hysterectomy, she will be required to use contraception until she has reached 6 weeks since the procedure.

^b For the purpose of defining the length of time of amenorrhea to determine postmenopausal status, only count time in which the woman was not taking medications such as oral contraceptives, hormones, gonadotropin-releasing hormone, anti-estrogens, SERMs, or chemotherapy that could induce transient amenorrhea.

8.2.4 Chest Radiography

A posterior-anterior chest x-ray (CXR), interpreted and reported by a radiologist or pulmonologist, will be obtained if there are relevant TB-related physical findings or other factors that the investigator feels warrant testing and imaging, as specified in the SoA (Section 1.3), and Section 8.2.6 of main protocol and Section 8.2.6 in this appendix. A posterior-anterior CXR may be obtained at Visit 1 at the investigator's discretion, if clinically indicated for TB infection. A lateral chest x-ray can also be obtained if, in the opinion of the investigator, a lateral view is indicated. Patients with documentation of a CXR, read by a qualified radiologist, that is sufficient for TB evaluation according to local standard of care, performed within 3 months before initial screening, may not need to repeat CXR at screening, based on the judgement of the

investigator. In either case, the CXR film(s)/image(s) or a radiology report must be available to the investigator for review. A computed tomography (CT) scan can be performed as an alternative to the CXR based on regional standard of practice. An IGRA or TST should also be performed (Section 8.2.6 of main protocol and Section 8.2.6 in this appendix).

8.2.6. Tuberculosis Testing

Initial Screening

All participants will be evaluated for risk factors for LTBI at rollover from their originator studies during the AMAX Visit 1 (Section 10.5, Appendix 5). If the participant has risk factors or any TB-related signs or symptoms are identified as part of the discussions of preexisting conditions or as part of the standard physical exam, the investigator should conduct a thorough physical examination, including body temperature measurement and assessment of peripheral lymph nodes. For participants with relevant TB-related physical findings or other factors that the investigator feels warrant testing and imaging:

- a TB test should be performed:
 - IGRA (for example, QuantiFERON-TB Gold or TSPOT.TB), or
 - Tuberculin skin test (TST; also called a purified protein derivative [PPD] or Mantoux test).

Participants from the Czech Republic will be screened for active and latent TB infection (LTBI) at Visit 1. This will include the following:

- Medical history of ongoing adverse events from originator study (Visit 1).
- Clinical assessment of risk (Section 10.5, Appendix 5).
- Physical examination as described in Section 8.2.2, and include body temperature measurement and assessment of peripheral lymph nodes.
- A test to assess immune response to mycobacterial antigens such as interferon- γ release assay (interferon gamma release assay [IGRA], for example, QuantiFERON-TB Gold or T-SPOT.TB).
- If a tuberculin skin test (TST) or purified protein derivative test is performed, the test will be at a designated location (a pulmonary outpatient clinic) and read by a pulmonologist.

Note: Source documentation must include the original laboratory report (for IGRA) or a record of the size in millimeters of the induration response (for TST). A TST recorded as “negative” without documenting the size of induration in millimeters will not be acceptable and will require a retest.

If participant has a history of positive TB test result with prophylaxis, TB testing should not be performed unless advised to do so based on local guidelines (See also section on Prior Treatment for LTBI).

- a CXR may should be performed if clinically indicated, as described in Section 8.2.4. A CT scan may be performed as an alternative to the CXR based on regional standard of practice.

Monitoring for TB during the study

For all participants, monitoring for TB is to be continuous throughout the study. Every 2 to 3 months as indicated in the SoA, the participants will be assessed for risk factors for TB (Section 10.5, Appendix 5). If the participant has a risk factor or any TB-related signs or symptoms identified as part of the AE discussions or standard physical exam, the investigator should conduct a thorough exam to evaluate for TB, including examination of peripheral lymph nodes and documentation of body temperature. If there are relevant physical findings or other factors that the investigator feels warrant testing and imaging, an IGRA OR TST and CXR should be performed. A CT scan can be performed as an alternative to the CXR, based on regional standard of practice.

Participants from the Czech Republic will also be screened for active and latent TB infection at yearly interval visits V9, V14, and V19 over the duration of the study (and throughout continued access if they participate), following all steps described above for Initial Screening, with medical assessment of all ongoing adverse events and with testing.

10.15.4. Hungary

This section describes protocol changes applicable for participants in study sites in Hungary.

This table describes the changes and provides a rationale for the changes

Protocol Section Number and Name	Description of the Change	Brief Rationale
1.1 Synopsis	Added additional information for participants in Hungary who were in the placebo group at Week 52 of AMAM and considered responders at Week 52 of AMAM	Updated in accordance the comments from the Medical Research Council, Ethics Committee for Clinical Pharmacology of Hungary
4.1 Overall Design	Added additional information for participants in Hungary who were in the placebo group at Week 52 of AMAM and considered responders at Week 52 of AMAM	Updated in accordance the comments from the Medical Research Council, Ethics Committee for Clinical Pharmacology of Hungary
7.2 Participant Discontinuation/Withdrawal from the study	Added AMAX participant discontinuation/withdrawal from study details for participants in Hungary who were in the placebo group at Week 52 of AMAM and considered responders at Week 52 of AMAM	Updated in accordance the comments from the Medical Research Council, Ethics Committee for Clinical Pharmacology of Hungary

The revised text in the following sections show the changes applicable for adult participants at study sites in Hungary.

1.1. Synopsis

Overall Design

Study AMAX is a Phase 3, multicenter, long-term extension study evaluating the efficacy and safety of mirikizumab in participants with moderately-to-severely active CD who have participated in an originator adult mirikizumab CD study, inclusive of the Phase 3 Study AMAM and the Phase 2 Study AMAG.

Participants who are CCI [REDACTED]

[REDACTED] for an extended period of time (up to 3 years) and then enter a 12- to 16-week posttreatment follow-up period. Participants who are CCI [REDACTED]

[REDACTED] after completion of the long-term extension period, if mirikizumab is not yet locally commercially available and reimbursable, eligible participants will be provided with an option of continued access to open-label mirikizumab, followed by a 4-week follow-up period. The duration of the continued access will differ by participant and country.

Participants who meet all of the inclusion criteria and none of the exclusion criteria of AMAX, and who, in the opinion of the investigator, would receive benefit from open-label treatment with mirikizumab are eligible for enrollment into Study AMAX. It is possible that some participants enrolling from Study AMAM may have received placebo only in the originating study. These participants will receive mirikizumab for the first time in Study AMAX. After the AMAM final database lock, the sponsor will unblind the treatment assignments of Hungary participants from Study AMAM. To comply with the response from the Medical Research Council, Ethics Committee for Clinical Pharmacology of Hungary, any Hungary sites that have participants who were in the placebo intervention group at Week 52 of Study AMAM and were considered responders at Week 52 of Study AMAM will receive a notification through the investigator to discontinue the participant from Study AMAX. These participants will complete the AMAX Early Termination Visit (ETV) and enter the posttreatment Follow-up Period.

4.1. Overall Design

Study AMAX is a long-term study of adult participants completing studies AMAM or AMAG (see schema in Section 1.2).

Two intervention groups will be studied in participants with moderate-to-severe CD:

- Mirikizumab CCI [REDACTED]
- Mirikizumab CCI [REDACTED]

CCI [REDACTED]

CCI [REDACTED]. After the AMAM final database lock, the sponsor will unblind the treatment assignments of Hungary participants from Study AMAM. To

comply with the response from the Medical Research Council, Ethics Committee for Clinical Pharmacology of Hungary, any Hungary sites that have participants who were in the placebo intervention group at Week 52 of Study AMAM and were considered responders at Week 52 of Study AMAM will receive a notification through the investigator to discontinue the participant from Study AMAX. These participants will complete the AMAX ETV and enter the posttreatment Follow-up Period.

CCI

Study participants will receive mirikizumab for an extended period of time (approximately 3 years or until commercial availability of mirikizumab, whichever comes first) and then enter a 12- to 16-week posttreatment follow-up period. After completion of long-term extension period, if mirikizumab is not yet locally commercially available and reimbursable, eligible participants will be provided with an option of continued access to open-label mirikizumab, and then enter a 4-week follow-up period (Section 10.13, Appendix 13). The duration of the continued access will differ by participant and country.

AMAM participants will require an endoscopy to be performed at Week 52, **CCI** in the AMAX study.

AMAG participants who are entering AMAX after completing **CCI** into AMAX. Participants who have not yet completed **CCI**

See Section 8.1.1.2 for details.

7.2. Participant Discontinuation/Withdrawal from the Study

Participants will be discontinued (withdrawn) from the study in the following circumstances:

- enrollment in any other clinical study involving an investigational product or enrollment in any other type of medical research judged not to be scientifically or medically compatible with this study
- participation in the study needs to be stopped for medical, safety, regulatory, or other reasons consistent with applicable laws, regulations, and good clinical practice (GCP)
- the investigator decides that the participant should be discontinued from the study
- all participants from originator Study AMAM **CCI** and enter the 12- to 16-week posttreatment follow-up period, or
- following the final database lock in Study AMAM, all participants in Hungary who were in the placebo intervention group at Week 52 of Study AMAM and who were considered responders at Week 52 of Study AMAM will be discontinued from Study AMAX

through a notification to the investigator and will complete the ETV and enter the posttreatment Follow-up Period, or

- the participant requests to be withdrawn from the study.

Participants discontinuing from the study prematurely for any reason should have AE and other safety follow-up specified for the ETV. See Section 1.3 (Schedule of Activities), Section 8.2 (Safety Assessments), and Section 8.3 (Adverse Events and Serious Adverse Events).

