Study AMAM was a Phase 3, multicenter, randomized, double-blind, double-dummy, parallel group, and active- and placebo-controlled, treat-through clinical trial of mirikizumab in participants with moderately to severely active CD. Participants who had an inadequate response to, loss of response to, or were intolerant to corticosteroid or immunomodulator therapy for CD (termed “conventional-failed”), and those who had an inadequate response to, loss of response to, or were intolerant to biologic therapy for CD (termed “biologic-failed”) were included in the study. The primary objective was to test the hypothesis that mirikizumab is superior to placebo as assessed by the following co-primary endpoints:

- PRO clinical response at Week 12 and endoscopic response at Week 52, and
- PRO clinical response at Week 12 and clinical remission by CDAI at Week 52.

A significantly greater percentage of participants achieved both co-primary endpoints at Week 52 in the mirikizumab group (endoscopic response: 38.0%, 220 of 579 participants, $p < 0.000001$; clinical remission: 45.4%, 263 of 579 participants, $p < 0.000001$) compared with the placebo group (endoscopic response: 9.0%, 18 of 199 participants; clinical remission: 19.6%, 39 of 199 participants).

Thus, mirikizumab demonstrated statistically significant and clinically meaningful improvements for both co-primary endpoints compared to placebo. Overall, higher frequencies of TEAEs were reported in the placebo group compared with the mirikizumab group. Most TEAEs were mild-to-moderate in severity. Frequency of SAEs and discontinuation due to AEs were higher in placebo group compared with the mirikizumab group. Three participant deaths were reported in this study (1 in the placebo group due to pulmonary embolism, 1 in the ustekinumab group due to sepsis, and 1 due to CD in the placebo nonresponder group who switched to mirikizumab at Week 12).

Additional nonclinical and clinical trial data are summarized in the Investigator's Brochure (IB).

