9.4.1.4. Missing Data Imputation

While every effort will be made to reduce missing data, the missing data imputation methods described below will be used to assess the efficacy endpoints when participants are permanently discontinued from study drug or otherwise have missing data.

- Nonresponder imputation (NRI): For analysis of categorical efficacy and health outcomes variables, missing data will be imputed using an NRI method. Participants will be considered a Nonresponder for the NRI analysis if they
 - do not achieve the endpoint(s) being analyzed
 - have missing data at the time point of interest that results in nonassessment of (an) endpoint(s) at the time point of interest, or
 - discontinue treatment prior to the time point of interest due to reasons other than participants switching to commercially available mirikizumab or extraordinary circumstances, e.g., inability to supply study drug to a particular region
- Mixed-model for repeated measures: For continuous variables, the analysis may include the MMRM with the missing-at-random assumption for handling missing data. This analysis takes into account both missingness of data and the correlation of the repeated measurements. Additional details will be provided in the SAP.
- Modified Baseline Observation Carried Forward with ANCOVA: For continuous variables, single imputation will be used based on carrying the baseline observation forward. Additional details will be provided in the SAP.

Additional details and sensitivity analyses, including imputed and observed data, will be specified in the SAP.

Methodology to address missing data due to participants switching to commercially available mirikizumab or extraordinary circumstances, e.g., inability to supply study drug to a particular region, will be addressed in the SAP.

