5.1.4 Definition of Study Intervention by Study Period

The table below provides the study intervention groups to be displayed for each analysis population and analysis period.

Analysis	Analysis Period	Study Intervention Groups:
Population		
PAS/mITT/Safety population	Induction Period/Complete Study Period/ Continued Access Period	 AMAM miri/miri/ SC AMAM pBO/miri/ SC AMAM PBO/miri/ IV AMAM PBO/miri/ IV AMAM uste/uste/ SC AMAM uste/uste/ IV AMAM PBO/PBO/ SC AMAM PBO/PBO/ IV AII AMAM/ SC a All AMAM/ IV a All AMAM a All AMAM/ SC a Total a
PAS/mITT subset populations	Complete Study Period	PAS/mITT sub-population – Endoscopic Responder in the originating study: • AMAM miri/miri/ SC (co-primary analysis) • AMAM PBO/miri/ SC • AMAM uste/uste / SC • AMAM PBO/PBO/ SC • All AMAM SC a • Total a PAS/mITT sub-population – Endoscopic Nonresponder in the originating study: • AMAM miri/miri / IV • AMAM PBO/miri/ IV • AMAM uste/uste / IV • AMAM PBO/PBO/ IV • AMAM PBO/PBO/ IV • All AMAM IV a • Total a

Analysis Population	Analysis Period	Study Intervention Groups:		
		Other sub-population analysis:		
		 AMAM miri/miri/ SC AMAM miri/miri/ IV AMAM PBO/miri/ SC AMAM PBO/miri/ IV AMAM uste/uste/ SC AMAM uste/uste/ IV AMAM PBO/PBO/ SC AMAM PBO/PBO/ IV AII AMAM/ SC a All AMAM/ IV a All AMAM a All AMAM a Total a 		

Abbreviations: AMAG = Study I6T-MC-AMAG; AMAM = Study I6T-MC-AMAM; IV = intravenous; miri = mirikizumab; PBO = placebo; SC = subcutaneous; uste = ustekinumab; Q4W = every 4 weeks.

For endpoints utilizing the PAS/mITT subset populations, not all intervention groupings listed above may be shown.

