5.1.5 Missing Data Imputation

Intercurrent events (FDA 2017) are events which occur after the study intervention initiation and make it impossible to measure a variable or influence how it should be interpreted. Section 1.1 includes intercurrent events for the primary and secondary endpoints. The missing data methods described below may be used to address the intercurrent event strategies proposed for this study.

Non-Responder Imputation

A hybrid estimand strategy will be used to handle binary endpoints:

- Patients who discontinue study treatment due to reasons other than commercial availability and extraordinary circumstances including study treatment supply issues and the site termination, are categorized as treatment failures after discontinuation. As such, these patients are not considered missing from the perspective of the estimand of interest.
- The hypothetical strategy will be used to handle the ICE of study treatment discontinuation due to commercial availability and extraordinary circumstances including study treatment supply issues and the site termination. Participants with the ICE will be excluded from analysis for timepoints of interest after the ICE. The assumption behind this approach is that measurements after this ICE are missing completely at random and thus the estimation can be implemented using observed values.

^a Unless otherwise specified, these treatment arms are not included in the modeling to estimate treatment effect for MMRM and ANCOVA analysis. Also these treatment arms may be excluded from some tables or figures to simplify the output.

A small number of patients who completed study treatment up to the time point of interest but are sporadically missing the binary endpoint data will still require imputation. These patients will be imputed using NRI.

Modified Baseline Observation Carried Forward (mBOCF)

As a primary analysis for continuous variables, the ANCOVA with mBOCF approach will be used for handling missing data. For continuous endpoints a hybrid estimand strategy is used:

- For ICEs of study intervention discontinuation due to reasons other than commercial
 availability and extraordinary circumstances including study treatment supply issues and
 the site termination, the composite strategy will be used such that measurements after the
 ICEs will return to baseline. As such, these patients are not considered missing from the
 perspective of the estimand of interest.

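### The ethics-mandated withdrawal of Hungarian placebo responders is not a named intercurrent event, so by default it is scored as treatment failure and lowers later rates in the descriptive placebo/placebo SC group

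*Protocol*

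**What the plan says.** **The withdrawal.** The Hungarian version of Protocol 7.2, in Appendix 10.15.4, adds a withdrawal criterion that applies once the final AMAM database is locked: "all participants in Hungary who were in the placebo intervention group at Week 52 of Study AMAM and who were considered responders" at that visit leave AMAX, complete an early termination visit and enter follow-up. The Hungarian synopsis gives the reason: "To comply with the response from the Medical Research Council, Ethics Committee for Clinical Pharmacology of Hungary". No efficacy or safety finding in AMAX is involved.

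**The scoring rule.** For binary endpoints, SAP 5.1.5 addresses "Patients who discontinue study treatment due to reasons other than commercial availability and extraordinary circumstances including study treatment supply issues and the site termination" and states that they "are categorized as treatment failures after discontinuation". SAP 1.1 defines the estimand in the same way. For continuous endpoints, values after such an event return to baseline. Protocol 9.4.1.4 has the same structure; its exceptions are a switch to commercial mirikizumab and "extraordinary circumstances, e.g., inability to supply study drug to a particular region". None of these texts mentions the Hungarian withdrawal.

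**The sensitivity analyses.** The mNRI analysis in SAP 5.1.5 uses multiple imputation for the same exceptions and scores all other discontinuations as non-response. The as-observed analysis drops anyone without data at the visit.

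**The group.** SAP 2 assigns AMAM participants to SC or to IV followed by SC by their endoscopic response at AMAM Week 52. SAP 5.1.4 lists "AMAM PBO/PBO/ SC" as a reporting group, which also feeds the pooled All AMAM SC and Total rows.

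**The concern.** The estimand already treats some stops as external to the drug's effect: a patient who moves to commercial product, or whose site closes, is not called a failure. The Hungarian withdrawal is external in the same sense. It was fixed in advance, applies to one country, and depends on AMAM arm and AMAM Week 52 status rather than on anything that happens in AMAX. A participant who still meets the endpoint on the day of withdrawal is nevertheless counted as not meeting it at every later visit.

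At stake is the interpretability of the long-term rates in the placebo/placebo SC group, and to a small degree the pooled SC row. The group is small, so a few such cases would matter. The error can only go downward. A reader of the tables could take it for loss of response.

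**Working it through.** **1. The plan's own figures.** Protocol 2.2.5 reports the AMAM endoscopic co-primary on placebo as "18 of 199 participants": 18/199 = 9.0%, which reproduces. This endpoint combines PRO response at Week 12 with endoscopic response at Week 52. Protocol 9.2 expects 50% to 70% rollover, or 640 to 900 participants: 640/0.50 = 1280 and 900/0.70 = 1286, which agree.

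**2. Group size n.** Protocol 2.2.5 mentions placebo nonresponders who switched to mirikizumab at Week 12, so the 18 approximate the endoscopic responders who stayed on placebo. Applying the overall rollover to them is an assumption: 18 × 0.50 = 9 and 18 × 0.70 = 12.6, about 13. At full rollover n is about 18. It could be slightly more, because footnote 2 to the analysis-set table in SAP 4 ignores AMAM concomitant-medication events when it forms subpopulations.

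**3. Formula.** Let k be the Hungarian cases withdrawn before a visit and x the responders among the n − k who remain. Scored as failures, the rate is x/n. Excluded after the event, as for the existing exceptions, it is x/(n − k). The ratio of the two is (n − k)/n, so the relative loss is k/n whatever the true rate.

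| n | k = 0 | k = 1 | k = 2 | k = 3 |
|---|---|---|---|---|
| 9 | 0% | 11% | 22% | 33% |
| 13 | 0% | 8% | 15% | 23% |
| 18 | 0% | 6% | 11% | 17% |

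The documents do not give k; these values only show the range.

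**4. Worked example.** Assume n = 13, k = 2 and a rate near 80% among those who remain, so x = 9.
- As failures: 9/13 = 69.2% (Wilson 95% interval 42.4% to 87.3%).
- Excluded after the event: 9/11 = 81.8% (52.3% to 94.9%).
- Difference: 12.6 points.

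**5. Pooled All AMAM SC row.** Its size N is not given. Assume N = 200 to 300 and an 80% rate. The drop in points is 80 × k/N: from 80 × 1/300 = 0.27 to 80 × 3/200 = 1.2 for k = 1 to 3.

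**6. Which analyses are affected.** NRI and mNRI both score these cases as failures, so comparing the two cannot reveal the problem. The as-observed analysis avoids it, but it also drops everyone else with missing data, so it does not isolate the effect.

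**The case against.** The strongest objection is that extraordinary circumstances is an open class. The SAP introduces its examples with the word including, and the protocol with e.g.; a national order that ends access to study drug could be placed there. That reading is possible. But the stated examples are supply and site failures, whereas this withdrawal was written into the protocol in advance for one country, and nothing assigns it to the exception. The SAP is based on the protocol amendment that carries the Hungarian text. Without an explicit statement, the failure rule applies.

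Several limits also stand:
- The number of cases is unknown and may be zero.
- Only visits after withdrawal are affected, and the final AMAM lock date is not given. Anyone who passed AMAX Week 52 before withdrawal keeps that result.
- The readable Hungarian text does not define responder. If it is not endoscopic response, some cases may fall outside the SC group.
- The study makes no formal comparisons, the pooled rows are outside the models by default, and the shift in the example lies within the interval for so small a group.
- Discontinuation reasons are to be summarised by AMAX and AMAM intervention (SAP 5.2), so the cause would be visible if it is coded separately.

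A reader might infer more than the documents support. The primary result is not biased: SAP 5.1.4 defines the co-primary group as mirikizumab/mirikizumab SC, and none of these participants is in it. Participants are not removed for doing well in AMAX; the trigger is status on placebo at AMAM Week 52. And 18 is not a ceiling on the group, for the reason given under the group-size step.

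**Conclusion.** The point holds in a limited form. By default the SAP scores an ethics-mandated withdrawal, unrelated to outcome in AMAX, as failure or return to baseline. For any k of at least 1, the placebo/placebo SC rate at visits after withdrawal is pulled down by a relative k/n, about 6% to 11% per case for n between 18 and 9. The pooled SC row moves by about 0.3 to 1.2 points under the assumptions shown. This rests on responder meaning endoscopic responder, on the overall rollover range applying to this group, and on at least one Hungarian case withdrawn before the visit. The harm is to a descriptive secondary group, not to the co-primary result. It still goes beyond missing detail, because a stated rule produces the wrong score unless the SAP says otherwise.

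**What to change.** In SAP 1.1 and 5.1.5, name the ethics-committee-mandated withdrawal in Protocol 10.15.4 (Hungary) as an intercurrent event under the hypothetical strategy: excluded from later time points in the NRI and mBOCF analyses, and multiply imputed in mNRI. Give it its own discontinuation reason code, state what responder means in that rule, and report the number of cases by reporting group. This changes only the analysis; it takes no position on the withdrawal rule itself.

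The cost is one phrase in two SAP sections, one reason code and one line in the disposition table. Statistically, the denominator becomes slightly smaller and the SAP's missing-completely-at-random assumption extends to these cases. Within placebo/placebo SC that is reasonable if responder means endoscopic responder, because withdrawal then depends only on country. In the pooled SC row it is less clean, because withdrawal also depends on AMAM arm; the reported count lets a reader judge how much that matters.
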